#### 1.2. Participants

The study comprised a total of 58 subjects divided into two groups of 29 individuals with similar characteristics (Table 2). To participate in the study, subjects were required to be between 18 and 65 years of age and body mass index (BMI) between 18.5 and 30 kg/m2. Participants also had to avoid all of the exclusion criteria: use of antibiotics in the last 3 months; use of medication for hypertension or for the treatment of hyperlipaemia; consumption of pre- or probiotic supplements; consumption of omega-3 or omega-6 supplements; eating , intestinal or similar problems; diabetes mellitus, chronic kidney disease, liver disease, infectious diseases or any type of cancer; having donated blood in the last month; having undergone surgery within the last three months; abusive alcohol consumption; being vegetarian; being pregnant; being a smoker; and participation in other clinical trials in the last 3 months.

		0 1	
	Control	Intervention	p-value 
Age (years)	$26.6 \pm 11.5$	$26.7 \pm 11.7$	0.97
Men	15	14	1.00
Women	14	15	1.00
BMI (kg/m2)	$23.7\pm2.7$	$23.6\pm2.8$	0.98
Weight (kg)	$66.6 \pm 11.8$	$68.4 \pm 12.7$	0.58
Fat mass (%)	$26.0\pm9.0$	$26.9\pm9.0$	0.71
Total colesterol (mg/dl)	$175.8 \pm 34.6$	$178.0 \pm 30.9$	0.80
Oxidized LDL (ng/mL)	$238.6 \pm 52.1$	$233.6 \pm 52.4$	0.71

Table 1. Distribution of volunteer demographics
---

 $^1$  p-values between control and intervention groups were examined using a one-way analysis of variance (Tukey's test). The results are shown as mean  $\pm$  SD (n=29).

# 1.3. Study Analyses

## **1.3.1.** Anthropometric measurements

The anthropometric analysis of the participants followed the protocol of the International Society for the Advancement of Kinanthropometry (ISAK). The following measurements were taken with the corresponding equipment: height (213 measuring rod, Seca deutschland, Germany), weight (body fat monitor with scale BF400, OMRON Healthcare, Japan), body mass index (BMI) and percentage of fat mass (body fat monitor BF306, OMRON Healthcare, Japan). Abdomen circumference was also measured (201 antrophometric tape, Seca deutschland, Germany). In addition, hip and waist circumferences were measured to calculate the waist:hip ratio (WHR) (cm waist:cm hip), which is used to evaluate the development cardiovascular disease.

# **1.3.2. Blood samples**

Subjects fasted for 12 hours prior to blood collection and were not allowed to perform moderateintensity exercise in the previous 24 hours. Blood samples were collected from the antecubital vein in gel and clot activator tubes (Vacutest Kima Srl, Arzergrande, Italy). These samples were centrifuged at 3500 rpm for 5 min at 4 °C to separate the serum from the cell fraction. After collection, the serum portions were stored at -80 °C until further analysis.

Biochemical markers such as basal glucose, GOT, GPT, hs-CRP and lipid markers (triglycerides (TG), LDL-C, HDL-C, and total cholesterol (TC)) were measured using a clinical chemistry analyzer (BA400 Biosystems).

Interleukin (IL) 1β, IL-6, IL-10, and tumour necrosis factor-alpha (TNFa) were analysed using commercially available kits (Milliplex Human High Sensitivity T Cell; Life Science, Darmstadt, Germany) according to manufacturer's indications. Catalase activity was assessed by an automatic method previously described by Slaughter et al. FRAP measurement was based on the method described by Benzie and Strain, with some modifications. Glutathione peroxidase (GPx) was determined using a commercially available method (Ransel, Randox Laboratories Limited, Crumlin, United Kingdom). Catalase, FRAP and GPx were measured in an automated chemistry analyzer (Olympus AU400, Olympus Diagnostica Europe GmbH, Ennis, Ireland). The TBARS assay was determined using commercially available ELISA Kit (Human ox-LDL(Oxidized Low Density Lipoprotein (ox-LDL) was determined using commercially available ELISA Kit (Human ox-LDL(Oxidized Low Density Lipoprotein) ELISA Kit, Texas, USA). TBARS and ox-LDL were measured using a microplate reader (Powerwave XS, Biotek instruments).

#### 1.3.3. Stool samples

Faecal samples were collected by participants at home, using a sterile kit provided to them previously. Once the sample was collected, participants stored it under refrigeration (for no more than 24-48h) until it was delivered to the researchers. Once received, it was stored at -20°C until the corresponding analyses were performed.

#### 1.3.3.1. Sample preparation for FRAP and short chain fatty acids analysis.

The faecal sample was previously defrosted at 4°C for 24h. Then, samples were diluted 1:10 with 0.1M phosphate buffer (2.33 g PO4HNa2 and 14.03 g PO4H2Na in 2L of water, pH 7.4) and sterilised. The mixture was centrifuged for 20 min at 5000 rpm in order to collect the supernatant and centrifuged again for 10 min. The supernatant was collected again and separated into 2 fractions for SCFA and FRAP assay analysis. The sample for AGCC was stored at -80°C until use. The FRAP assay was performed on the same day of sample preparation.

#### 1.3.3.2. FRAP assay.

The antioxidant capacity of faeces was measured using the FRAP assay, according to the procedure described by Benzie and Strain. For this purpose, the supernatant portion was previously diluted with water at 1:10 dilution.

#### 1.3.3.3. Short chain fatty acids analysis

The production of SCFAs was assessed according to the procedure described in Panzella et al. with some modifications. The supernatant portion was filtered through 0.20  $\mu$ m PTFE filters and analysed by reversed-phase HPLC with diode array detector (1260 Infinity II LC System, Agilent, Santa Clara,

CA, USA). The results were obtained in ppm and converted to mmol/kg faeces, expressing the result as the increase of SCFAs in 24 hours.

# 1.3.3.4. DNA extraction and metagenomic sequencing

Bacterial genomic DNA was isolated from each fermentation pellet sample using NZY Soil gDNA Isolation kit (Nzytech, Lisboa, Portugal). Sequencing of the V3 and V4 regions of the 16S rRNA gene was performed on the MiSeq (Illumina, Essex, UK) instrument using 2 x 300 bp reads. The oligonucleotide primers targeting the 16S rRNA gene V3 and V4 regions were 5'-TCGTCGGCAGCGTCAGATGTGTATAAGAGACAGCCTACGGGNGGCWGCAG-3' and 5'-GTCTCGTGGGCTCGGAGATGTGTATAAGAGACAGCAGCCTACHVGGGTATCTAATCC-3',

respectively. The 16S-V4 sequencing library was first reviewed with FastQC for overall quality assessment, and the libraries were processed in R package DADA2 (v.1.8.0.). Reads were quality trimmed with the "filterAndTrim" function with "maxEE (2,5)" and reads below 165 bp were discarded. Forward and reverse reads are merged below to generate a table of sequences, and the resulting Amplicon Sequence Variants (ASVs) were subjected to de novo chimera detection, using DADA2 and any artifacts were removed.

#### 1.3.3.5. Bioinformatic analysis

For bacteria taxonomic assignment, ASVs were queried against the Silva database v.132 [The SILVA ribosomal RNA gene database project: improved data processing and web-based tools] using IDTAXA implemented in the R package DECIPHER. Sequences identified as non-bacterial were discarded.

The abundance matrix, the taxonomy assignment and the metadata obtained from each sample were merged and imported with the phyloseq v3.12 package. Alpha diversity was calculated in R using the phyloseq package, and several alpha indices were generated, such as ASV numbers, Chao1, ACE, Shannon, Simpson, InvSimpson, and Fisher and plotted using the function "plot richness". Beta diversity was calculated using weighted and unweighted Unifrac distances. To test for significant differences in community composition among different seasons, permutational multivariate analysis of variance using distance matrices (PERMANOVA) was conducted using the Adonis function in the R package, and the results were visualized by Principal Coordinates Analysis (PCoA).

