#### 1.1. Trial Design

This study consisted of a double-blind, randomised, controlled, unicentric trial with two parallel arms depending on the cooked meat product consumed (control and reformulated), with a duration of 5 weeks. The study was approved, according to the Declaration of Helsinki, by the Bioethics Committee of the University of Murcia (UMU) with code 550/2023. The research took place at the Department of Nutrition and Bromatology of the Faculty of Veterinary Medicine of the University of Murcia. Investigators provided a detailed explanation of the protocol to participants, and those choosing to participate gave their informed consent. Each participant received a unique code based on their arrival order. Following this, an external researcher then assigned the participants to the different groups with the aim of having two similar groups based on sex, age, and IMC. The specific group assignments were not known to either the researchers or the participants.

Three weeks before the start of the study, a recruitment phase was carried out, in which potential participants were recruited and informed about the details of the study. From a total of 63 individuals initially recruited, fifty-eight volunteers completed the trial. Participants who abandoned the trial were for personal reasons unrelated to the study. Two visits were made during the experimental phase of the intervention: the initial and the final visit. At both visits, blood, faeces, and urine samples were obtained from participants, and anthropometric measurements were also taken. Two deliveries of 15 blister packs of 100g control or reformulated cooked meat product were made, at baseline and after 17 days. Individuals consumed one blister pack per day for 6 days per week. Throughout the trial, subjects recorded their complete diet in a collection notebook, which was given to the researchers at the end of the study.

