#### 1.4. Statistical analysis

Data analysed were expressed as mean  $\pm$  standard deviation (SD). Student's t-test was used to analyse significant differences over time (baseline and final). To analyse the differences between groups in the evolution of the different variables, an analysis of variance (ANOVA) was performed for repeated measures, with time (baseline and final) as the within-subject factor, and the product consumed (Control and Intervention) as the between-subject factor. Tukey's test was carried out for post hoc analysis. Cross-tabulation and chi-square tests were conducted to determine the perception of respondents on food additives based on demographic data.

Data processing and statistical analysis were performed using SPSS version 28.0 (IMB Corp., Armonk, NY, USA) with a significant level of  $p \le 0.05$ .

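### The only stated test of gut community composition (PERMANOVA) compares seasons, a factor this trial does not have, so as written it does not address the product effect

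*Protocol*

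**What the plan says.** Protocol section 1.3.3.5 first sets the distance measure: "Beta diversity was calculated using weighted and unweighted Unifrac distances". The test follows: "To test for significant differences in community composition among different seasons, permutational multivariate analysis of variance using distance matrices (PERMANOVA) was conducted". It was run with the Adonis function in R and displayed by principal coordinates. The protocol states no other test of community composition.

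The design is described elsewhere in the protocol:

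- Section 1.1 describes a trial "with two parallel arms depending on the cooked meat product consumed (control and reformulated), with a duration of 5 weeks", with an initial and a final visit. On sampling it says: "At both visits, blood, faeces, and urine samples were obtained from participants".
- Section 1.2 reports "a total of 58 subjects divided into two groups of 29 individuals with similar characteristics".
- Section 1.4 states the aim of the main comparison, "To analyse the differences between groups in the evolution of the different variables", and meets it with a repeated-measures ANOVA "with time (baseline and final) as the within-subject factor, and the product consumed (Control and Intervention) as the between-subject factor". The software named there is SPSS.

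**The concern.** A PERMANOVA p-value is a statement about the factor put into the model. Here the protocol names a factor that the trial does not contain. Followed literally, the test cannot be run, because no season variable exists. Followed loosely, it could mean product, visit, or a combination of the two, and these answer different questions. A reader given a PERMANOVA result from this trial could not tell from the protocol whether it concerns the reformulated product.

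This is a stated hypothesis that conflicts with the design. It is not a detail that the protocol leaves open for a statistical analysis plan to fill.

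**Working it through.** The protocol gives no sample size, power or effect figure for this test, so there is no figure to reproduce. The check sets the sections side by side and then asks what each reading of the sentence would test.

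**Step 1. Factors in the design.** Product has 2 levels (sections 1.1, 1.2 and 1.4). Time has 2 levels (sections 1.1 and 1.4). That gives 2 × 2 = 4 cells of 29 samples. If all 58 completers gave both faecal samples, there are 58 × 2 = 116 samples.

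**Step 2. Factors in the test.** Section 1.3.3.5 names season only. Of the 2 design factors, 0 are named.

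**Step 3. Does section 1.4 fill the gap?** Its ANOVA names the right two factors, but it analyses one variable at a time in SPSS. It can cover each alpha-diversity index, since each is one number per sample. It cannot take a matrix of pairwise distances, which is why section 1.3.3.5 gives a separate method in R. The product contrast is therefore not stated for community composition.

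**Step 4. What each reading would test.** Let d_C and d_R be the mean change from baseline to final in the control and reformulated arms, as vectors in the space of the distances. Euclidean geometry is assumed here in place of UniFrac, to show the principle. With 29 participants per arm:

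- *Season read as visit.* The mean change over all 58 is (d_C + d_R)/2, and the sum of squares is 2 × 58 × |half the mean change|² = (58/2) × |(d_C + d_R)/2|² = 29 × |(d_C + d_R)/2|².
- *Product-by-time.* Each of the 4 cells departs from additivity by (d_R − d_C)/4, up to sign, so the sum of squares is 4 × 29 × |d_R − d_C|²/16 = (58/8) × |d_R − d_C|² = 7.25 × |d_R − d_C|².

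Suppose both arms change by the same d. The visit term is 29 × |d|² and the product-by-time term is 7.25 × 0 = 0. Now suppose the arms change by −d and +d. The visit term is 29 × 0 = 0 and the product-by-time term is 7.25 × |2d|² = 29 × |d|². The visit term depends only on the average change over both arms, so it carries no information on how the arms differ.

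- *Season read as product group.* The test would concern the product, and only the wording would be wrong. It would still be unclear whether final samples alone or all samples were compared. With all samples pooled and no difference at baseline, a final difference of δ enters as (0 + δ)/2 = δ/2.

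Only the product-by-time reading matches the aim stated in section 1.4.

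**The case against.** The strongest reply is that this is a slip of wording. Neighbouring sections support that. Section 1.3.3.4 takes DNA from fermentation pellets and section 1.3.3.3 reports short-chain fatty acids as a 24-hour increase, although the stool sections describe no fermentation step. This suggests methods text carried over from other work. Sections 1.1 and 1.4 leave no doubt about the real factors, and the analyst may well have used them. This stands as the likely explanation. It does not repair the sentence, because nothing in the protocol says which term was run.

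A reader might go further and infer that a wrong test was carried out, or that a change common to both arms was reported as a product effect. The document supports neither: it shows no result and no model call.

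A reader might also argue from the calendar that the trial is too short to contain different seasons. That does not hold. Section 1.1 says "Three weeks before the start of the study, a recruitment phase was carried out", which dates the phase without giving its length. Faeces were taken only at the two visits, and a short window can still cross from one season to the next. The sound point is simply that season is not a factor of the design.

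It can also be said that a permutation scheme is commonly left to the statistical analysis plan. That is fair, and its absence is not the defect. It appears in the fix because anyone rewriting the sentence has to deal with two samples per participant.

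**Conclusion.** The point holds as a wrong statement of the analysis. The only stated test of community composition names a factor that the trial lacks, and no other section supplies the right one. As written, it does not address the product effect.

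The size is that 0 of 2 design factors are named, in one test of one outcome domain. The blood, anthropometric, urine and other single-variable analyses under section 1.4 are untouched, and the protocol does not designate community composition as primary. No error rate or loss of power can be attached to the trial. Such a figure would need an assumed reading of season, together with shift sizes and within-person correlations that the protocol does not give.

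The conclusion rests on one modest reading: that the PERMANOVA was run on the UniFrac distances named just before it, since no other distance is given. It should be fixed, and it is cheap to fix.

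**What to change.** In section 1.3.3.5, remove the reference to seasons and state that PERMANOVA on the weighted and unweighted UniFrac distances tests the product-by-time contrast (control versus reformulated, baseline versus final). Add that permutations keep each participant's two faecal samples together, for example by permuting product labels between whole participants.

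If the analysis has already been run, as the past tense suggests, state which term was tested. Re-run it only if that was not the product contrast.

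The cost is one sentence and, if a re-run is needed, one changed model term and permutation scheme in R. No new data are required.

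### The Adonis test of community composition names a factor this trial does not have and states no permutation restriction for paired stool samples; if both visits are pooled and permuted freely, its p-values would be distorted in both directions

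*Protocol*

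**What the plan says.** Section 1.1 (Trial Design) has two visits and states: "At both visits, blood, faeces, and urine samples were obtained from participants". Section 1.2 (Participants) states: "The study comprised a total of 58 subjects divided into two groups of 29 individuals".

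Section 1.3.3.5 (Bioinformatic analysis) merges the abundance, taxonomy and per-sample metadata into one object. It then says "Beta diversity was calculated using weighted and unweighted Unifrac distances" and introduces the community test with the purpose "To test for significant differences in community composition among different seasons". The method is given as "permutational multivariate analysis of variance using distance matrices (PERMANOVA) was conducted using the Adonis function in the R package". There is no model formula, participant term, strata or blocks, no number of permutations, and no statement of which visits enter.

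Section 1.4 (Statistical analysis) recognises the pairing for the ANOVA: "an analysis of variance (ANOVA) was performed for repeated measures, with time (baseline and final) as the within-subject factor", with product as the between-subject factor. That section describes analyses in SPSS and does not mention the community test in R.

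**The concern.** Two things are wrong or left open in the same sentence of section 1.3.3.5.

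- **The factor.** The trial has a product factor (control or reformulated) and a time factor (baseline or final). It has no season factor. As written, the test does not address the trial's question.
- **The pairing.** Two samples from one person are expected to resemble each other. A permutation test that shuffles all samples freely treats them as exchangeable. Product varies between people, so its true sampling spread is larger than the shuffled reference, and false positives rise. Time and product-by-time vary within people, so their true spread is smaller than the reference, and real effects are missed.

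This is the only stated test of whether the product shifted community composition. A significant product separation could merely reflect stable differences between individuals. A real change due to the product, which appears as product-by-time, could go unseen. Correcting the factor name alone would not cure this.

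**Working it through.** The protocol gives no figure for this test, so there is none to reproduce. The check asks what free permutation would do if both visits were pooled.

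**Inputs**
- From section 1.2: 58 participants, 29 per arm.
- From section 1.1: two stool samples each, so up to 58 × 2 = 116.
- From section 1.4: significance level 0.05 (stated for the SPSS analyses and applied here).
- Assumed, not in the protocol: within-person correlation ρ (the between-person share of total variance), number of dimensions and their variance pattern. Euclidean distance stands in for UniFrac.

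**One-dimensional approximation.** Let each sample have variance σ².
- Product difference, both visits pooled: each person's mean has variance σ²(1+ρ)/2, so the difference between arms has variance 2 × σ²(1+ρ)/(2 × 29) = σ²(1+ρ)/29.
- Time difference: each person's change has variance 2σ²(1−ρ), so the mean change over 58 people has variance 2σ²(1−ρ)/58 = σ²(1−ρ)/29. Product-by-time carries the same factor (1−ρ).
- Free permutation compares both with about σ²(1/58 + 1/58) = σ²/29.

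The null rejection rate at nominal 5% is therefore about 2[1 − Φ(1.96/√(1+ρ))] for product and 2[1 − Φ(1.96/√(1−ρ))] for time and product-by-time:

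| ρ | 1.96/√(1+ρ) | Product | 1.96/√(1−ρ) | Time, product-by-time |
|---|---|---|---|---|
| 0 | 1.960 | 5.0% | 1.960 | 5.0% |
| 0.3 | 1.719 | 8.6% | 2.343 | 1.9% |
| 0.5 | 1.600 | 11.0% | 2.772 | 0.6% |
| 0.7 | 1.503 | 13.3% | 3.578 | 0.04% |

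**Simulation, 1 to 50 dimensions** (pseudo-F, 199 permutations, 500 null data sets per setting). The first three result columns are the product test under free permutation:

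| ρ | 1 dim. | 10 dim. | 50 dim. | Time and product-by-time, free, all dimensions |
|---|---|---|---|---|
| 0 | 4.8% | 3.8% | 3.4% | 4-7% |
| 0.3 | 8.6% | 14.4% | 22.0% | 0-3% |
| 0.5 | 9.8% | 22.0% | 34.4% | 0-0.6% |
| 0.7 | 15.0% | 25.8% | 54.4% | 0% |

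The one-dimensional column agrees with the formula within simulation error. The product distortion grows with dimension because the pseudo-F sums over axes. When whole participants were permuted for product and interaction, and visits were swapped within participants for time, all three tests rejected in 3-8% of data sets.

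**Other variance patterns**
- With 10 to 50 dimensions and ρ of 0.3 to 0.7, another run gave 12-33% for product and 0-1.3% for time and product-by-time. Permuting product labels on within-person change, or on final samples alone, gave 4-7%.
- With 20 to 50 dimensions, a further run gave 15-33%, 25-54% and 35-65% for product at ρ of 0.3, 0.5 and 0.7.

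**Power for product-by-time**
- Ten dimensions, assumed time shift of 0.4 SD and interaction of 0.6 SD on the first axis: 9% with free and 55% with restricted permutation at ρ = 0.5; 3% and 72% at ρ = 0.7.
- Assumed 0.5 SD product effect on three axes: 6-25%, 0-13% and 0-4% with free permutation at ρ of 0.3, 0.5 and 0.7, against 39-56%, 58-67% and 83-93% when product labels are permuted on within-person change.

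**The case against.** The strongest case is that the protocol does not say samples were shuffled freely. Naming a function does not reveal its arguments, and permutation detail may sit in an analysis plan that is not shown. Nor does section 1.3.3.5 say that both visits enter one model. A comparison of final samples alone would fit the text and has no pairing problem. Section 1.3.3.4 adds doubt about the unit: "Bacterial genomic DNA was isolated from each fermentation pellet sample", with no number per person or visit. Product, time and product-by-time are not named for this test either.

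All of that stands, and it makes the pairing concern conditional. A reader might infer four stronger things that the document does not support:
- **That 116 samples were permuted freely.** This is inferred from silence.
- **That the p-values are necessarily far off.** The size depends on an assumed correlation and dimension. At ρ = 0.3 in one dimension the product test rejects in about 9% of null data sets, and at ρ = 0 there is no distortion.
- **That a product-by-time effect could hardly be detected.** Power under free permutation still reached 25% in one setting at ρ = 0.3.
- **That this is the only formal microbiota test.** The ANOVA in section 1.4 may cover the alpha-diversity indices.

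The objection does not remove the point. The season factor is an error on the page. The section otherwise fixes the analysis in detail and in the past tense, and section 1.4 shows that the pairing was recognised for other outcomes but not carried over to this one.

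**Conclusion.** The point holds in conditional form. It is certain that section 1.3.3.5 names a factor the trial does not have and states no permutation restriction, although section 1.1 has stool samples at both visits. If both visits are pooled and permuted freely, product p-values would tend to be too small and time and product-by-time p-values too large.

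For assumed correlations of 0.3 to 0.7 and 10 to 50 dimensions, product would be declared different in about 12-33% of null trials at nominal 5%. Across the other dimensions and variance patterns tried, the range is 9-65%. Time and product-by-time would be declared in about 0-1%, or up to 3% in one dimension. These figures rest on Euclidean coordinates in place of UniFrac and on a correlation the protocol does not give. The direction follows from any positive correlation; the size is uncertain.

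**What to change.** In section 1.3.3.5:
1. Replace the season factor with the trial's factors, and state which samples enter and how many per participant and visit.
2. Test the product effect on each participant's baseline-to-final change in UniFrac principal-coordinate space, permuting product labels across whole participants. A simple valid alternative is PERMANOVA on the final samples alone, one per participant. Change has variance 2σ²(1−ρ) against σ² for a final sample, so it is the more precise choice when ρ exceeds 0.5.
3. Test time only by swapping the two visits within a participant.
4. Report no product p-value from freely permuted pooled visits.

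The cost is a few lines of R on data already held. The downside is that a pooled product p-value may become less favourable. If the analysis already used final samples alone or restricted permutations, stating so and correcting the factor name would settle the point.
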